## **3 STUDY DESIGN**

### **3.1 Overall Study Design**

This is a double-blind, randomized, placebo-controlled study to assess the efficacy, safety, and tolerability of serlopitant for the treatment of pruritus in adults with plaque psoriasis. Subjects who meet the study entry criteria will be randomized in a 1:1 ratio to receive daily

oral doses of serlopitant 5 mg or placebo for 8 weeks. The study will be conducted at approximately 40 study sites in North America.

The study will consist of three periods, for a total study period of approximately 12 or 14 weeks:

- Screening period: 2 or 4 weeks
- Treatment period: 8 weeks
- Follow-up period: 2 weeks

During the screening period, subjects will undergo eligibility evaluation and will have their baseline symptom scores established. Subjects who require a washout of prior therapies per study criteria will perform their Screening visit 4 weeks prior to randomization. Subjects who do not require a washout of prior therapies can perform the Screening visit 2 weeks prior to randomization. Subjects will be provided an electronic diary (eDiary) at screening and are expected to complete the diary daily for the duration of the study. Subjects must be willing and able to complete the electronic diary within a consistent timeframe on a daily basis, to wear actigraphy devices during sleep, and to comply with restrictions on allowable concomitant therapies for the duration of the study.

At the Baseline visit (Day 1), eligible subjects will be randomly assigned to receive serlopitant 5 mg or placebo. Subjects will take a loading dose (3 tablets taken orally) at the site on the first day of the treatment period (Day 1). Starting on Study Day 2, subjects will take one tablet per day taken orally. Serlopitant may be taken with or without food.

The primary efficacy endpoint will be assessed at Week 8 of treatment.

After completion of the treatment period or early discontinuation of study drug, all subjects will enter a 2 week follow-up period.

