## **5.6 Study Drug Discontinuation**

Subjects should be discontinued from study drug treatment in the following situations:

- A female subject becomes pregnant
- The subject decides to discontinue study drug treatment, or withdraw consent from the study
- The subject receives a strong CYP3A4 inhibitor
- The subject receives an excluded medication for treatment of pruritus or psoriasis
- Any medical condition that may jeopardize the subject's safety if study drug is continued, in the investigator's and/or Sponsor's opinion
- Discontinuation is deemed to be in the best interest of the subject, in the investigator's and/or Sponsor's opinion
- The subject experiences a NCI CTCAE Grade 3 or higher treatment emergent AE that is assessed as likely related to study drug

The Sponsor or designee should be contacted within 24 hours of investigator's awareness of any study drug treatment discontinuation. Investigators should make every effort to contact the Sponsor or designee before discontinuing study drug treatment, if possible.

Subjects who discontinue treatment with study drug prior to completing the treatment period will have a Follow-up visit 14 days after their last dose of study drug (see [Section 6.5.9](#)). Every effort should be made for subjects to complete the Follow-up visit after a subject has discontinued from study drug.

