### **6.5.9**            *Follow-up Visit*

For all subjects, the Follow-up visit occurs 14 days (+ 3 days) after the Week 8 visit or the last dose of study drug for subjects who discontinue study drug early. Every effort should be made for subjects to complete the Follow-up visit after a subject has discontinued study drug early. At the Follow-up visit, the following procedures and assessments are to be performed:

- Concomitant medications
- Adverse events
- Targeted physical exam
- Vital signs (including weight)
- ECG
- Laboratory
  - Hematology
  - Chemistry
  - Urine pregnancy test for females of childbearing potential (with positive or equivocal results confirmed by a serum pregnancy test)
  - Urinalysis
  - Endocrine
  - Reproductive endocrine labs for females for females under 55 years of age at consent
- BSA
- PGA
- sPGA
- PGIC
- PIQ
- eDiary review
- Study drug compliance (if not previously performed for subjects who discontinued study drug early)
- Collect study drug (if not previously performed for subjects who discontinued study drug early)
- Collect eDiary and actigraphy watches

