## **8.2 Handling of Missing Data and Excluded Therapy Use**

Should a determination of treatment period (on treatment, pre-treatment) be required for adverse events or concomitant medication but the corresponding date is missing, or is a partial date, the event/medication will be considered on treatment unless the portions of the date that are available indicate this is not possible.

The primary method of handling missing efficacy data will be MCMC multiple imputation. Imputation will be conducted within each treatment group independently, so the pattern of missing observations in one treatment group cannot influence missing value estimations in another. For each imputation process, 25 imputations will be performed.

If a subject fails to complete their eDiary for a week or more the primary endpoint (WI-NRS), may be missing. If the Week 8 measure from the eDiary is unavailable because the subject withdrew from the study due to lack of efficacy, or the subject uses an excluded therapy to treat psoriasis or pruritus, their responder status will be defined as non-responder. If the Week 8 value is missing for any other reason, the WI-NRS change from baseline value will be based on imputed data. Missing Week 8 WI-NRS values from which the 4-point responder status is derived will be estimated by MCMC.

Missing WI-NRS data will be derived for the analysis using the method of MCMC multiple imputation. Since both primary and key secondary endpoints require WI-NRS, the following steps will be followed:

1. Using the daily eDiary data, calculate Baseline and Week 2 through Week 8 values by averaging available values. If any values are available, these will be used i.e. a minimum of 1 observation is required to compute a week's average.
2. From step 1, create a dataset for each treatment group, of subjects with observed values and those needing estimation by MCMC. The missing WI-NRS values in each dataset will be filled in using the MCMC method to generate 25 datasets.

The resulting datasets for each treatment arm will be combined into one complete dataset.

Syntax:

```
proc mi data=datain out=dataout seed=&seed. Nimpute=25 <options>;  
  where trtpn=(TRT); /* Note TRT = [1, 2]; depending on treatment group */;  
  mcmc chain=single;  
  var baseline d2 d3 d4 d5 d6 d7 week2 week3 week4 week5 week6 week7 week8;  
run;
```

3. From each complete dataset, the dichotomous responder rate will be determined.

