### **8.3 Analysis Populations**

Primary efficacy analyses will be based upon an intent-to-treat (ITT) philosophy. The primary efficacy population will be the Full Analysis Set (FAS), which will include all randomized subjects who received at least one dose of study drug. Subjects will be analyzed within the treatment group to which they are randomized.

The primary safety population will be all treated subjects with at least one post-baseline assessment. For safety analyses, subjects will be classified based upon the treatment received.

Additional analyses performed on the Per Protocol (PP) population will be considered supportive. The PP population will include all subjects in the safety population who complete the Week 8 evaluations without any significant protocol violations (i.e., any subject or investigator activity that could have possibly interfered with the therapeutic administration of the treatment or the precise evaluation of treatment efficacy). The PP population will include subjects in the safety population who do not meet any of the following criteria:

- Violated the inclusion/exclusion criteria;
- Received a strong CYP3A4 inhibitor (See [Appendix B](#));
- Received an excluded medication which may plausibly impact the primary endpoint at Week 8
- Have not been compliant with the dosing regimen (i.e. subjects must comply with 80–120% of the expected dosage of study medication during participation in the study);
- Have not completed Week 8 visit within  $\pm 7$  days window

Subjects who discontinue from the study drug due to an adverse event related to study treatment or documented lack of treatment effect, or who met protocol-defined non-responder criteria, will be included in the PP population. Prior to breaking the blind, other additional criteria may be added to the lists above to accommodate for unforeseen events that occurred during the conduct of the trial that result in noteworthy study protocol violations.

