**Table 3                    Schedule of eDiary and Actigraphy Assessments**

eDiary and actigraphy devices are provided to subjects at the Screening visit. eDiary and actigraphy devices are collected at the Follow-up Visit.

Device	Assessment	Frequency and Duration of Assessment	Comments
eDiary	WI-NRS	Once daily from Screening visit through the Follow-up visit.	
eDiary	Dosing	Once daily from Baseline visit through Week 8 visit or study drug discontinuation.	
Actigraphy watch	Scratching	Continuous nighttime monitoring from Screening visit through the Follow-up visit.	Download data and replace watches at each study visit.
Actigraphy watch	Sleep	Continuous nighttime monitoring from Screening visit through the Follow-up visit.	Download data and replace watches at each study visit.

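### A subject who stops study drug by about Day 32 hands back the eDiary before Week 8, so the primary endpoint must be imputed even if the subject was willing to keep recording

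*Protocol*

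**What the plan says.** **Path after an early stop.** Protocol 3.1: "After completion of the treatment period or early discontinuation of study drug, all subjects will enter a 2 week follow-up period". Section 5.6 says that these subjects "will have a Follow-up visit 14 days after their last dose of study drug". Section 6.5.9 adds a window of +3 days: "the Follow-up visit occurs 14 days (+ 3 days) after the Week 8 visit or the last dose of study drug" for those who stop early.

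**End of diary collection.** Table 3 in Appendix A schedules the WI-NRS "Once daily from Screening visit through the Follow-up visit" and states that "eDiary and actigraphy devices are collected at the Follow-up Visit". The procedure list in 6.5.9 has the same step: "Collect eDiary and actigraphy watches". Nothing in the protocol keeps an off-drug subject on the diary or the visit schedule up to Week 8.

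**Status of these subjects.** Section 6.6 recognises only loss to follow-up and withdrawal of consent as early termination from the study. Stopping study drug is neither, and several triggers in 5.6 (for example a likely related Grade 3 event, or a strong CYP3A4 inhibitor) say nothing about willingness to continue the diary.

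**Endpoint and missing data.** The Week 8 value is the mean of that week's daily home scores, and one entry is enough (8 and 8.2). Withdrawal from the study for lack of efficacy, or use of an excluded therapy for psoriasis or pruritus, makes the subject a non-responder. Otherwise: "If the Week 8 value is missing for any other reason, the WI-NRS change from baseline value will be based on imputed data". Section 8.3 states: "Primary efficacy analyses will be based upon an intent-to-treat (ITT) philosophy".

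**The concern.** The primary endpoint is one question answered at home each day, and it needs no clinic visit. The schedule nevertheless stops asking it at a point fixed by the last dose, so a stopper's Week 8 outcome is observed or imputed according to when the drug was stopped. A subject who stops at Day 42 for an adverse event contributes a full, observed, off-drug Week 8. A subject who stops at Day 25 for the same reason contributes an imputed one.

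The imputation in 8.2 is run within arm on baseline, d2-d7 and week2-week8, with no variable for being off drug. Its late-week relationships are therefore learned mainly from subjects still taking the tablets. In the serlopitant arm this tends to carry some on-drug benefit into stoppers; stopping placebo has no matching effect. What is at stake is a modest and avoidable reliance on imputation in the primary analysis. An SAP cannot repair it later, because the data are never collected.

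**Working it through.** **1. The plan's own figure.** The protocol states no cut-off day. Its only related figure is 90% power with 100 per group (8.1). An unstratified two-proportion test reproduces it: 0.903 for 24% vs 43.5% at one-sided 5%, and 0.909 for 24% vs 46% at one-sided 2.5%. This point does not change the sample size.

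**2. Cut-off day.** Inputs: Follow-up visit 14 to 17 days after the last dose (6.5.9); at least one entry needed (8.2); Week 8 assumed to be Days 50-56; an entry on the visit day counts.

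Last diary day = last-dose day + 14 to + 17.
Earliest last dose giving one entry = 50 - 17 = Day 33, up to 50 - 14 = Day 36.
Earliest last dose giving all seven = 56 - 17 = Day 39, up to 56 - 14 = Day 42.

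| Last dose | Last diary day | Week 8 entries |
|---|---|---|
| Day 25 | 39-42 | 0 |
| Day 32 | 46-49 | 0 |
| Day 33 | 47-50 | 0-1 |
| Day 35 | 49-52 | 0-3 |
| Day 36 | 50-53 | 1-4 |
| Day 39 | 53-56 | 4-7 |
| Day 42 | 56-59 | 7 |

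With Week 8 as Days 51-57, the one-entry cut-off moves to Day 34-37. If the week is tied to a Week 8 visit held 3 days early or late, the range is about Day 30-39. Collecting the device before that day's entry adds one day.

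**3. Share of the arm affected.** The protocol gives no discontinuation rate for this trial. In the prurigo nodularis study (1.4.3), 9 of 128 subjects stopped for TEAEs: 3 on serlopitant and 6 on placebo. With 1:1 allocation the serlopitant share is about 3/64 = 4.7%. If stops are spread evenly over 56 days (an assumption), the share by Day 32-35 is 4.7% x 32/56 to 35/56 = 2.7% to 2.9%, about 3%. Stops for other reasons would add to this. I use 3-5%.

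**4. Size of the bias.** Overstatement = share affected x (imputed responder rate - true off-drug rate), with the true off-drug rate assumed to be the placebo rate of 24%.

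- Upper illustration, imputing at the full on-drug rate: gap 43.5 - 24 = 19.5 points. A share of 3% gives 0.6 points, 5% gives 0.98 and 10% gives 1.95.
- Allowing for the subject's own scores: a stopper at Day 25 has diary data to Day 39-42, so Week 5 (Days 29-35) and four to seven days of Week 6 (Days 36-42) are observed off drug and enter the model. An illustrative normal model (weekly SD 2.5, week-to-week correlation about 0.8-0.92, effect fading over 7 days; all assumptions) gives imputed rates of about 26-37%, a gap of 2-13 points. Then 3% x 2 = 0.06 and 5% x 13 = 0.65 points.

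**5. Whether this could change the conclusion.** With 24 of 100 placebo responders, an unstratified one-sided chi-squared test gives p = 0.060, 0.044, 0.032 and 0.023 for 34, 35, 36 and 37 serlopitant responders. The middle category of the decision rule is two responders wide. A bias below one responder per 100 matters only for a result lying at a boundary.

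**The case against.** The strongest reply is that this is a coherent Phase 2 design. Sections 3.1, 5.6, 6.5.9 and Table 3 agree in substance. The intent-to-treat sentence in 8.3 introduces who is analysed and in which arm; it does not promise collection after study drug is stopped. That stands: the documents do not contradict themselves here, and I claim only a poor fit.

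A reader might infer that early stoppers are imputed as if still on drug, near 43.5%, which would inflate the serlopitant rate by 1-2 points. The documents do not support that. The model in 8.2 uses each subject's own weekly scores with no on-treatment restriction, and the follow-up period supplies about two off-drug weeks. With the half-life of 45-86 hours in 1.4.1, 14 days (336 hours) is about 4 to 7 half-lives. Nor does the figure of 9 of 128 (7%) describe the serlopitant arm, where only 3 of about 64 stopped for TEAEs.

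A reader might also infer that every subject who stops early lacks a primary outcome. Those covered by the two non-responder rules have one whatever the day of stopping.

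Finally, extending the diary alone would create a new problem. Sections 5.7 and 5.7.2 tie therapy recording and restrictions to the end of the follow-up period. A subject who stopped at Day 10 has the Follow-up visit at Day 24-27, could then start an excluded therapy unrecorded, and could count as an observed responder. That objection is right, and the fix has to deal with it.

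**Conclusion.** The point holds as a cheap improvement to the collection schedule; it is not an error that threatens the trial. For a subject who stops study drug without withdrawing consent, a last dose on or before Day 32 leaves no Week 8 entry, Days 33-35 may leave none, and a full week needs a last dose on or after about Day 39-42. These days assume Week 8 is Days 50-56; other definitions shift them by a few days.

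Outside the two non-responder rules, the value is then imputed within arm with no off-drug indicator. The direction probably favours serlopitant but is not certain. At 3-5% of the arm, the overstatement is probably below 1 percentage point. A figure of 1-2 points needs both 5-10% affected and imputation at the full on-drug rate, so it is an upper illustration. The schedule gap itself does not depend on these assumed rates; only its size does.

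**What to change.** - **Sections 5.6, 6.5.9 and Table 3:** state that a subject who stops study drug but does not withdraw consent keeps the eDiary and records the WI-NRS daily through Day 56. Leave the 14-day Follow-up visit unchanged and have the device returned later.
- **Section 5.7:** for these subjects, extend the recording of concomitant and excluded therapy use to Day 56, for example at the Week 6 telephone contact and one telephone contact at Week 8. This concerns recording only, so that the existing non-responder rule can still be applied.
- **Section 8.2:** use the observed Week 8 scores of these subjects in the FAS analysis, with the non-responder rules as they are. Imputation then covers only subjects who really stop recording.

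Cost: a few more weeks of one-question diary entries, one or two telephone contacts and a later device return for a handful of subjects. No extra clinic visit and no change in sample size. The change has to be made before devices are collected, because the scores cannot be recovered afterwards.

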## **6.6 Early Termination**

Early termination of a subject from the study may occur due to the following reasons:

- lost to follow-up
- withdrawal of consent by the subject

In accordance with legal requirements and International Conference on Harmonisation (ICH) – Good Clinical Practice (GCP) guidelines, every subject or his/her legal representative has the right to withdraw from the study at any time and without providing reasons. If a subject is willing to provide a reason for withdrawal, this will be recorded in the electronic Case Report Form (eCRF). The Investigator or site staff must make every effort to contact subjects who are suspected of being lost to follow-up. A minimum of two attempted telephone contacts and a certified letter are required before a subject can be deemed as lost to follow-up. Attempts to contact such subjects must be documented in the subject's source documents.

## **7 ASSESSMENT OF SAFETY**

### **7.1 Definitions**

#### **7.1.1 Adverse Event**

An AE is any untoward medical occurrence associated with the use of a drug in humans, whether or not considered drug related. An AE can be any unfavorable and unintended sign (e.g., an abnormal laboratory finding), symptom, or disease temporally associated with the use of a drug, without any judgment about causality.

AEs include treatment emergent exacerbations of pre-existing illnesses and AEs that occur as a result of protocol-mandated interventions.

#### **7.1.2 Serious Adverse Event**

An SAE is considered “serious” if it results in any of the following outcomes:

- Death
- Life-threatening AE (i.e. the subject was at immediate risk of death from the event as it occurred. An event that might have led to death if it had occurred with greater severity is not “life-threatening”)
- Inpatient hospitalization or prolongation of existing hospitalization
- Persistent or significant incapacity or substantial disruption of the ability to conduct normal life functions

- Congenital anomaly/ birth defect
- Important medical event (i.e. an event that may not result in death, be life-threatening, or require hospitalization, but which may be considered serious by the investigator or Sponsor, as it may jeopardize the subject and may require medical/surgical intervention to prevent one of the outcomes listed above). Examples of such medical events include allergic bronchospasm requiring intensive treatment in an emergency room or at home, blood dyscrasias or convulsions that do not result in inpatient hospitalization, or the development of drug dependency or drug abuse.

The following are not considered SAEs: a visit to the emergency room or other hospital department < 24 hours that does not result in admission (unless considered an important medical or life-threatening event), an elective surgery planned prior to signing consent, admission as per protocol for planned medical/surgical procedure, and/or routine health assessments requiring admission for baseline/trending of health status (e.g., routine colonoscopy).

The terms “severe” and “serious” are not synonymous. Severity refers to the intensity of an AE (e.g., mild, moderate, or severe pain); the event itself may be of minor medical significance (e.g., severe back pain). “Serious” is a regulatory definition, as defined above. Seriousness (not severity) serves as the basis for defining regulatory reporting obligations.

Severity and seriousness should be independently assessed when recording AEs and SAEs on the eCRF.

### **7.1.3            *Abnormal Physical Exam, Laboratory, Vital Sign, and Electrocardiogram Findings***

Abnormal physical exam findings that are clinically significant and are identified prior to the first dose of study drug should be recorded as medical history. New or worsening clinically significant abnormal physical exam findings identified after the first dose of study drug should be recorded as AEs.

Only abnormal laboratory, vital sign, and ECG findings that are considered clinically significant by the investigator (e.g., require active management or are associated with accompanying symptoms/signs) will be recorded as medical history or AEs on the eCRF. Abnormal laboratory, vital sign, and ECG findings that occur prior to the first dose of study drug should be recorded as medical history, and abnormal findings that occur after the first dose of study drug should be recorded as AEs.

If the clinically significant laboratory, vital sign, or ECG abnormality is a sign associated with a confirmed disease or condition (e.g., elevated creatinine in a subject diagnosed with chronic kidney disease), only the diagnosis (chronic kidney disease) needs to be recorded on the AE eCRF.

Separate instances of the same clinically significant laboratory, vital sign, or ECG abnormality across visits should not be recorded as separate AEs or SAEs.

#### **7.1.4 Deaths**

Any deaths that occur from the time of informed consent to the Follow-up visit, regardless of attribution, must be reported within 24 hours of investigator's awareness of the death. See *MTI-109 SAE Report Form and Pregnancy Report Form Completion Guidelines* for complete instructions.

The Sponsor should be provided a copy of any post-mortem findings and/or relevant medical reports, including histopathology.

